### Sensitivity and Supportive Analyses

Sensitivity and specificity of CAPTURE score should be (score 3-6) vs (score 0-2) and (score 4-6) vs (score 0-3), respectively.

### Model Results Presentation

- Estimated sensitivity and specificity for Capture Score

### Endpoint(s)

Frequency of Clinically Important Deterioration (CID) composite outcome and its components

### Model Specification

- The CID will be derived from three key clinical assessments, which are 1) moderate/severe exacerbations 2) worsening of FEV1 and 3) worsening of health status using the CAT score.
- Definition of the composite CID event\*: moderate/severe exacerbation and/or  $\geq 2$ -unit deterioration from baseline in CAT score and/or  $\geq 100$  mL deterioration from baseline in FEV1 (CAT-containing CID).
- Two subgroups of participants were created based on CID status at Month 6, Month 18 and Month 30.
- CID status will be evaluated at visit 2/3/4.
- 

### Model Results Presentation

- Number and percentage of CID-positive and CID negative for each subgroup (GOLD I-IV, chronic bronchitis, healthy control) at each visit.

- Number and percentage of positive and negative response of each CID components (Exacerbation CID, FEV1 CID, CAT CID) at each visit for each subgroup

\*There are two definitions of CID: one is SGRQ-containing definitions; the other is CAT containing definitions, here we use CAT containing definitions, because we only have the baseline data for SGRQ, but we have both baseline and follow up data for CAT score.

Endpoint(s)

 
Time to the first CID composite event
 

Model Specification

 
The CID will be derived from three key clinical assessments, which are 1) moderate/severe exacerbations 2) worsening of FEV1 and 3) worsening of health status using the CAT score.
 
Definition of the composite CID event*: moderate/severe exacerbation and/or <math>\geq 2</math>-unit deterioration from baseline in CAT score and/or <math>\geq 100</math> mL deterioration from baseline in FEV1 (CAT-containing CID).
 
Two subgroups of participants will be created based on CID status at Month 6, Month 18 and Month 30.
 
CID status will be evaluated at visit 2/3/4.
 
Cox proportional hazards model
 
Terms in the model: 
 
Response: Time to the first CID composite event. 
 
Categorical: type of subjects (i.e. GOLD I-IV, chronic bronchitis, healthy control), gender, smoking status, site (type of hospital), maintenance therapy and ICS containing treatment
 
Continuous: age, baseline FEV1, baseline CAT score, count of COPD exacerbations
 
 
 
 
 
The actual time to the first deterioration, of each individual component and the composite endpoint, will be analyzed using a Cox's proportional hazards model, with the 'exact' method for handling ties. (If the analysis will not run using the 'exact' method, then the 'Efron' method for handling ties will be used instead.)
 
The time to the first deterioration based on the composite endpoint will be taken as the time to the first deterioration of any component event making up the composite.
 

Model Results Presentation

 
A Kaplan-Meier plot with estimates of the proportion of subjects with CID event over time will be produced for each type of subjects (i.e. GOLD I-IV, chronic bronchitis, healthy control) will be plotted on the same figure.
 
The ratio of the estimated hazard rates for the comparison between different type of subject will be presented with 95% confidence intervals.
 
Estimated probabilities of the occurrence of CID event at each visit will be shown with 95% confidence intervals for each type of subject.
 

Model Checking & Diagnostics

 
Refer to Appendix 7: Model Checking and Diagnostics for Statistical Analyses.
 

Endpoints
Rate of EXACT events
Model Specification

 
Generalized linear mixed model
 
In sub-cohort population.
 
Terms in the model: 
 
Response: definition of EXACT events: magnitude of responder for symptomatic events defined as acute, sustained symptomatic worsening of COPD, defined as an increase in EXACT score <math>\geq 9</math> points for 3 days or <math>\geq 12</math> points for 2 days, above baseline (average in 7-day period)
 
Dependent variable: Events response (Yes/No)
 
Categorical: month, type of subjects (i.e. GOLD I-IV, chronic bronchitis, healthy control), gender, smoking status, site (type of hospital), maintenance therapy (Y/N) and ICS containing (Y/N).
 
Continuous: age, baseline EXACT total score
 
Interaction: baseline*month
 
Repeated: month
 
 
 
The model will be fit with an unstructured variance-covariance matrix
 
For sub cohort population, visit 1 (month1-6) and visit 3 (month 18-23)
 

Model Results Presentation

 
Number and percentage of events and non-events for each subgroup (GOLD I-IV, chronic bronchitis, healthy control) at each month
 

Endpoint(s)
Change in Evaluating Respiratory Symptoms in COPD (E-RS: COPD) scores
Model Specification

 
Mixed Models Repeated Measures (MMRM) model.
 
While missing data are not explicitly imputed in the MMRM analyses, there is an underlying assumption that the data are missing at random.
 
The E-RS utilizes 11 respiratory symptom items from the existing and validated 14-item EXACT, which measures the symptoms of exacerbation with 3 subscales assess breathlessness, cough and sputum, and chest symptoms. Our analyses will include both the total score and the 3 subscale scores.
 
The MMRM analysis for E-RS scores measurements were available for sub-cohort at (months 1-6 and months 18-23).
 
Terms in the model: 
 
Response: Change in E-RS score at each visit.
 
Categorical: visit, type of subjects (i.e. GOLD I-IV, chronic bronchitis, healthy control), gender, smoking status, site (type of hospital), maintenance therapy (Y/N) and ICS containing (Y/N).
 
Continuous: age, baseline E-RS score
 
Interaction: baseline E-RS score*visit, type of subjects*visit
 
Repeated: visit
 
 
 

- The model will be fitted with an unstructured variance-covariance matrix.
- The Kenward and Roger method (KR) for approximating the denominator degrees of freedom and correcting for bias in the estimated variance-covariance of the fixed effects will be used.
- Baseline is defined in Section 5.2.

Two models will be fitted; one with a response variable of change from baseline and one with the response variable as the raw value.

### Model Results Presentation

- Least-square (LS) means and LS mean change from baseline values for each type of subject (Overall COPD subjects, GOLD I-IV, chronic bronchitis, healthy control) will be presented with their associated standard errors as well as 95% CIs. The estimated difference along with corresponding standard error, 95% CI for each visit will be presented.
- The LS mean differences (and associated 95% CIs) for all visits will also be presented graphically.

### Model Checking & Diagnostics

- Refer to [Appendix 7: Model Checking and Diagnostics for Statistical Analyses](#).

### Sensitivity and Supportive Analyses

A mixed effects model whereas time is entered as a random effect will be analysed as a supportive analysis to estimate the longitudinal changes if necessary.

### Endpoints

- Change from baseline in airway thickness by lung HRCT
  - Change in lung density by lung HRCT
  - Small airways disease measured using estimates of gas trapping

### Model Specification

- Similar to analyses of change in CAT score with MMRM
- In sub-cohort population.

### Model Checking & Diagnostics

- Refer to [Appendix 7: Model Checking and Diagnostics for Statistical Analyses](#).

### Endpoint(s)

- Change in physical activity measures (daily steps)

### Model Specification

- Mixed Models Repeated Measures (MMRM) model.
- While missing data are not explicitly imputed in the MMRM analyses, there is an underlying assumption that the data are missing at random.
- The MMRM analysis for daily steps were available for sub-cohort for one month period at visit 1 and visit 3 .
- Terms in the model:
  - **Response:** Change in daily steps.

- **Categorical:** week, type of subjects (i.e. GOLD I-IV, chronic bronchitis, healthy control), gender, smoking status, site (type of hospital), maintenance therapy (Y/N) and ICS containing (Y/N).
- **Continuous:** age, baseline daily steps
- **Interaction:** baseline daily steps\*week, type of subjects\*week
- **Repeated:** week
- The model will be fitted with an unstructured variance-covariance matrix.
- The Kenward and Roger method (KR) for approximating the denominator degrees of freedom and correcting for bias in the estimated variance-covariance of the fixed effects will be used.
- Baseline is defined in Section 5.2.

### Model Results Presentation

- Least-square (LS) means and LS mean change from baseline values for each type of subject (Overall COPD subjects, GOLD I-IV, chronic bronchitis, healthy control) will be presented with their associated standard errors as well as 95% CIs. The estimated difference along with corresponding standard error, 95% CI for each weeks will be presented.
- The LS mean differences (and associated 95% CIs) for all weeks will also be presented graphically.

### Model Checking & Diagnostics

- Refer to [Appendix 7: Model Checking and Diagnostics for Statistical Analyses](#).

### Subgroup Analyses

This will include analysis by age (<65 years,  $\geq 65$ ), gender (Female, Male), GOLD I-IV baseline reversibility, number of exacerbations in previous year (2, 3,  $\geq 4$ ) and smoking status (ever/never smoker).

### Sensitivity and Supportive Analyses

A mixed effects model whereas time is entered as a random effect will be analysed as a supportive analysis to estimate the longitudinal changes if necessary.

### Endpoint(s)

- Exacerbation in the 18 months in the full population

### Model specification

- Logistic regression with binary endpoint
- Response variable:
- moderate exacerbation in the 18 months period vs exacerbation free for 18 months in the full population
  - severe exacerbation vs exacerbation free or only moderate exacerbation for 18 months in the full population
  - moderate or severe exacerbation vs exacerbation free for 18 months in the full population
- Predictors/ covariates

- **Continuous variables:** age, Number of pack-years, Total SGRQ score, FEV1 % pred (post), FVC % pred (post), mMRC, CAT, Hemoglobin and remove (some of) aforementioned covariate(s) or add other covariate(s) if needed.
- **Categorical variables:** Gender, Smoking status (former vs never, current vs never), Education level (high school vs less high, above school vs less high), Type of hospital, Household income (low income  $\leq 80000$  vs high income  $> 80000$ ), GOLD grade (II vs I, III vs I, IV vs I), Neutrophil/lymphocyte ratio (low  $< 5$ , high  $\geq 5$ ), Eosinophils (low  $< 300$ , high  $\geq 300$ ), CRP (low  $\leq 3$ , high  $> 30$ ), Fibrinogen (low  $< 400$  high  $\geq 400$ ), Asthma diagnosed before age 40 (either in Medical History or Childhood Respiratory Asthma is diagnosed as yes, then labelled as yes), Moderate exacerbations in one year (yes or no), Severe exacerbations in one year (yes or no), history of CB (Has the subject had bronchitis or chronic coughing with phlegm or sputum from the chest, for at least past 2 years, and at least 3 months in past year), Diabetes (yes-no), Gastroesophageal Reflux and remove (some of) aforementioned covariate(s) or add other covariate(s) if need.
- The data set will be randomly participated into training dataset (approximate two thirds of the full sample size, adjusted if necessary) and testing dataset (approximate one third of the full sample size, adjusted if necessary).
- The training dataset is used to fit the model using the predictors significant in the univariate model ( $P < 0.05$ , the criteria can be adjusted if necessary).
- The testing dataset is used to evaluate the performance of the fitted model where the C-index will be calculated, the predictors of the testing dataset will be same as those of training dataset.

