| Protocol Activity   | Screen/Baseline | Study visit     |   |                 |   |   |
|---|-----------------|-----------------|---|-----------------|---|---|
|   |                 | X  | - | X  | - |   |
| Monthly CAT   | X  | -               | - | X  | - | - |
| Blood biomarkers (inclusive of serum sRAGE, CC16, IP-10, HbA1c) | X               | -               | - | X               | X | X |
| Sputum cytology                                    | X               | -               | - | X               | X | X |
| Sputum microbiome                                  | X               | -               | - | X               | X | X |

CAT=COPD assessment test, COPD=Chronic Obstructive Pulmonary Disease, HRCT=High-resolution computed tomography, EW=Early Withdrawal, EXACT=EXAceration of COPD Tool; SGRQ-C=St.George's Respiratory Questionnaire for COPD. CAPTURE=COPD Assessment in Primary Care to Identify Undiagnosed Respiratory Disease and Exacerbation Risk

1. Exacerbation visits only apply to subjects included in the Biomarker & Digital sub-cohort. Moderate exacerbations are defined as COPD exacerbations that require either systemic corticosteroids (intramuscular (IM), intravenous, or oral) and/or antibiotics. Severe exacerbations are defined as COPD exacerbations requiring hospitalization or result in death.
2. Informed consent must be conducted at the screen visit prior to performing any study procedures.
3. For COPD participants only;
4. When a trimonthly telephone interview overlaps a clinical visit, the COPD exacerbation assessment, COPD medication and treatment questionnaires will be completed at the clinic visit. A month is defined as 30 days in this study.
5. Data collection of COPD exacerbation assessment, COPD medication and treatment are not required for the healthy control participants.
6. CT scan should only be performed at withdrawal visit if the last study CT performed was more than a year ago. Inspiratory and expiratory HRCT scans are required at Visit 1 and Visit 4, while only inspiratory scan will be conducted on exacerbation visit. The CT scan for an exacerbation visit should only be performed if the last study CT scan performed was more than 14 days.
7. Pre-and post- bronchodilator values of spirometry test will be collected at each site visit.

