**CONFIDENTIAL**

Protocol Activity		Screen/Baseline	Study visit				
	CAT (Phone Call)	Trimonthly Phone Call 					
Healthcare resource utilization and cost		-	X	X	X	X	X
Assessments							
COPD exacerbation assessment (on site visit) 		-	X	X	X	X	X
COPD exacerbation assessment (Phone Call) 		Trimonthly Phone Call 					
COPD medication and treatment (on site visit) 		X	X	X	X	X	X
COPD medication and treatment (Phone Call) 		Trimonthly Phone Call 					
Death		-	X				
Serious Adverse Event assessment 			X	X	X	X	X
Lab							
Blood Draw for e.g. fibrinogen/HsCRP/Cell count		X	-	-	X	X	X
Sub-cohort only							
Lung HRCT scan 		X	-	-	X	X	X
Daily steps		X 	-	X 	-	-	-
Evening diary (EXACT plus additional questions)		X 	-	X 	-	-	-
Monthly CAT		X 	-	X 	-	-	-
Blood biomarkers (inclusive of serum sRAGE, CC16, IP-10, HbA1c)		X	-	-	X	X	X
Sputum cytology 		X	-	-	X	X	X
Sputum microbiome 		X	-	-	X	X	X

CAT=COPD assessment test, COPD=Chronic Obstructive Pulmonary Disease, HRCT=High-resolution computed tomography, EW=Early Withdrawal, EXACT=EXAcerbation of COPD Tool; SGRQ-C=St.George's Respiratory Questionnaire for COPD.

1. Exacerbation visits only apply to subjects included in the Biomarker & Digital sub-cohort. Moderate exacerbations are defined as COPD exacerbations that require either systemic corticosteroids (intramuscular (IM), intravenous, or oral) and/or antibiotics. Severe exacerbations are defined as COPD exacerbations requiring hospitalization or result in death.
2. Informed consent must be conducted at the screen visit prior to performing any study procedures.
3. For COPD participants only;
4. When a trimonthly telephone interview overlaps a clinical visit, the COPD exacerbation assessment, COPD medication and treatment questionnaires will be completed at the clinic visit.
5. Data collection of COPD exacerbation assessment, COPD medication and treatment is not required for the healthy control participants.
6. CT scan should only be performed at withdrawal visit if the last study CT performed was more than a year ago. Inspiratory and expiratory HRCT scans are required at Visit 1 and Visit 4, while only inspiratory scan will be conducted on exacerbation visit.

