## 4. ANALYSIS POPULATIONS

**Table 2. Summary of Study Populations**

Population	Definition / Criteria	Analyses Evaluated
Full population	The Full Population will consist of all subjects who are enrolled in the study and attend Visit 1.	
 
• Disease Progression Analyses
 
• Phenotypic Analyses
 
• Treatment Pattern and Healthcare Resource Utilization/Cost
 
• Safety Analyses
 

Population	Definition / Criteria	Analyses Evaluated
Sub-cohort population	Subjects who are enrolled in the Biomarker & Digital sub-cohort and who provided a least one additional sub-cohort assessment.	
 
• Disease Progression Analyses
 
• Phenotypic Analyses
 
• Treatment Pattern and Healthcare Resource Utilization/Cost
 
• HRCT analysis
 

Completer Population	The Completer Population will consist of all subjects in the Full Population who complete all scheduled clinic visits over 2.5 years.	
 
• Disease Progression Analyses
 
• Phenotypic Analyses
 
• Treatment Pattern and Healthcare Resource Utilization/Cost
 

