## 5. CONSIDERATIONS FOR DATA ANALYSES AND DATA HANDLING CONVENTIONS

### 5.1. Number of Participants and sub-groups

A total of 2,000 participants are planned to be enrolled, consisting of 1,700 participants with COPD, 180 with chronic bronchitis but without fixed airflow limitation, and 120 never smoker healthy control. Specifically, COPD subjects will be classified using the GOLD grades I – IV (i.e. mild, moderate, severe and very severe). To better understand the disease progression of early stage COPD, i.e. GOLD I and II grades, COPD participants will be recruited in the following manner: GOLD I: 700, GOLD II: 700, GOLD III: 200, GOLD IV: 100 ([Figure 1](#)[Error! Reference source not found.](#)).

[figure not shown]
Figure 1 Study Population Schematic

More assessments will be conducted among the 400 Biomarker & Digital sub-cohort participants who will be all recruited from selected Type A hospitals. The sub-cohort consists of 50 never smoker healthy control, 100 chronic bronchitis (N never smoker: 25), 100 GOLD I (N never smoker: 25), 100 GOLD II (N never smoker: 25) and 50 GOLD III participants (N never smoker: 20) ([Figure 2](#)[Sub-cohort Population Schematic](#)). In GOLD I-III grades, certain number of COPD participants with previous exacerbation history (i.e. exacerbators) will be recruited (target number of subjects are as follows - GOLD I: 60 exacerbators, GOLD II: 60 exacerbators, GOLD III: 30 exacerbators). Further, a proportion of those who are maintenance inhaler treatment naïve will be recruited, aiming for: 10 participants who are maintenance inhaler treatment naïve

will be recruited among exacerbators and non-exacerbators in each GOLD I, II, III groups respectively (Figure 2). All patient population sizes are approximate and allow +/- 10% for feasibility.

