### Demo examples for multivariate logistic regression of the full population

For the model using the predictors significant in the univariate model

```
ods graphics on;
ods output
CLparmWald=CLparmWald
FitStatistics=FitStatistics
ParameterEstimates=ParameterEstimates
RSquare=RSquare
ROCAssociation=ROCAssociation
proc logistic data=mulregdata;
/*the data set consists of response variable and significant
predictors in the univariate logistic model of all GOLD III and GOLD
IV */
model response variable(event='1')= x1-xn/rsquare cl;
/*significant predictors in the univariate logistic model of each
covariates set, i.e., set 1-4 will be fitted separately*/
run;
```

For the model using AIC and BIC criteria

```

ods graphics on;

ods output FitStatistics=FitStatistics
      ParameterEstimates=ParameterEstimates
      Association=Association;

proc hplogistic data= fullpopulationdata;
/*the dataset consists of all subjects of full population, each
covariates set, set 1-4 will be fitted separately */

model response variable(event='1') = all the listed
predictors/association ctable=Roc lackfit;

selection method=stepwise (SELECT=AIC CHOOSE=AIC STOP=AIC);
/*For BIC, change to (SELECT=BIC CHOOSE=BIC STOP=BIC) */

run;

```

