## 12.3. Appendix 3: Assessment Windows

### 12.3.1. Visit Based Assessments

Nominal visits (scheduled visit) will be used for reporting and analysis.

Assessment windows for the scheduled study visits are as follows:

Full population:

- Baseline/Screen (+ 3 days)
- Visit 2 ( $\pm$  28 days)
- Visit 3 ( $\pm$  28 days)
- Visit 4 ( $\pm$  28 days)

In addition, COPD and chronic bronchitis participants will be contacted by phone on trimonthly basis within  $\pm$  7 days of the planned date to assess the CAT and to collect information on exacerbation rates and COPD medications; healthy controls will be contacted by phone on trimonthly basis within  $\pm$  7 days of the planned date to assess the CAT only.

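### The 18-month exacerbation models use the full population, so the predictor screen may count healthy controls, who have no exacerbation follow-up, as event-free

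*SAP*

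**What the plan says.** The models are in RAP amendment 2, which follows SAP amendment 3 in the same file.

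- **Response and population.** RAP 7.4.1 defines three binary 18-month responses, all in the full population. The third is "moderate or severe exacerbation vs exacerbation free for 18 months in the full population". The training and testing sets are random fractions of the full sample.
- **Screen.** "The training dataset is used to fit the model using the predictors significant in the univariate model", at P<0.05, a threshold that may be adjusted.
- **Who is in the population.** RAP section 4: "The Full Population will consist of all subjects who are enrolled in the study and attend Visit 1". RAP 5.1 gives the planned make-up: "consisting of 1,700 participants with COPD, 180 with chronic bronchitis but without fixed airflow limitation, and 120 never smoker healthy control".
- **What is collected in controls.** Protocol section 2, footnote 5: "Data collection of COPD exacerbation assessment, COPD medication and treatment are not required for the healthy control participants". The SAP and RAP schedules repeat this. Under RAP 12.3.1 the controls' three-monthly calls are made within 7 "days of the planned date to assess the CAT only".
- **Code comments.** In the RAP's four-covariate-set analysis, the stepwise program carries the comment "the dataset consists of all subjects of full population". The comment on the univariate-screen program beside it refers to GOLD III and IV.

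No text removes healthy controls from these models or states their response value.

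**The concern.** Healthy controls have no exacerbation follow-up, and eligibility makes them differ from patients on several candidate predictors. They are never smokers with CAT below 10 and FEV1/FVC of at least 0.70. If they are entered as exacerbation-free, a univariate test of smoking, pack-years, CAT or FEV1 % predicted partly compares patients with controls, not patients who exacerbate with patients who do not.

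The first objective asks whether predictors of COPD progression found in Western cohorts apply in China. Variables selected partly because they mark the presence of disease do not answer that question.

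There is a second difficulty. GOLD grade is coded only as II, III and IV against I, and protocol 9.1 collects exacerbation history in COPD participants only. Screening and final fitting can therefore rest on different people without the plan saying so.

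**Working it through.** The plan gives no error rate or sample-size figure for these models, so there is no stated number to reproduce.

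**Inputs**
- Planned assessed participants: 1,700 COPD + 180 chronic bronchitis = 1,880. Healthy controls: 120, which is 6% of 2,000 (RAP 5.1).
- Training share of two thirds (RAP 7.4.1): 1,253 assessed and 80 controls.
- Never smokers capped at 30% in each COPD and chronic bronchitis group (protocol 5.2), so at least 70% are ever smokers. Controls: 0%.
- 18-month event risk among assessed participants: not in the documents. Assumed 5% to 50%.
- Controls coded event-free: an assumption, examined under the objection.

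**Closed form for ever against never smoking, with no true association among assessed participants.** The RAP uses former and current against never. I collapse these to ever against never for simplicity.

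With 70% ever smokers:
- Ever smokers: 0.7 × 1,253 = 877.1.
- Never smokers: 0.3 × 1,253 + 80 = 455.9.
- The event rate is p in ever smokers and p × 375.9/455.9 in never smokers, because the 80 controls add no events.
- Pass probability = Φ((d − 1.96·SE0)/SE1), where d is the rate difference, SE0 the pooled and SE1 the unpooled standard error.

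At p = 0.20:
- Never-smoker rate 0.1649; odds ratio (0.20/0.80)/(0.1649/0.8351) = 1.27.
- d = 0.03510, SE0 = 0.02256, SE1 = 0.02201.
- Φ((0.03510 − 0.04422)/0.02201) = Φ(−0.41) = 0.34.

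At p = 0.30:
- Never-smoker rate 0.2474; odds ratio 1.30.
- d = 0.05264, SE0 = 0.02598, SE1 = 0.02545.
- Φ((0.05264 − 0.05092)/0.02545) = Φ(0.07) = 0.53.

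Simulation with a logistic score test (2,000 replicates per cell) gives 35% and 52% for the same two cases.

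**Full range.** The odds ratios and first-line smoking pass rates are closed form. The dropout, continuous-predictor and controls-excluded rows are simulated.

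| Assumed 18-month risk | 5% | 10% | 20% | 30% | 50% |
|---|---|---|---|---|---|
| Spurious odds ratio, 70% ever smokers | 1.22 | 1.24 | 1.27 | 1.30 | 1.43 |
| Pass rate, 70% ever smokers | 10% | 17% | 34% | 53% | 86% |
| Same, after 25% dropout | 10% | 14% | 28% | 41% | 76% |
| Pass rate, 85% ever smokers | 15% | 31% | 62% | 85% | 99% |
| Continuous predictor, control mean 1 SD away | 8% | 9% | 18% | 27% | 55% |
| Continuous predictor, control mean 2 SD away | 12% | 22% | 48% | 71% | 98% |
| Continuous predictor, controls excluded | 4% | 5% | 4% | 6% | 5% |

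A continuous predictor whose control mean lies 0 to 0.25 SD away passes in about 4% to 8% of runs.

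**Where controls remain after the screen.** Controls and chronic bronchitis participants have no GOLD grade and no COPD exacerbation history. Complete-case fitting drops them from any model with either variable. That includes the AIC and BIC models on the main list, where both are candidates. Covariate sets 3 and 4 omit GOLD grade, so controls stay there if blank history is coded as no, or if the history variables are not retained.

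**Sub-cohort.** The planned control share is 50/400 = 12.5%, and that screen may be relaxed to P<0.1.

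**The case against.** The strongest reply is that the plan never codes controls as event-free. Uncollected data are blanks under the missing-data appendix, logistic procedures drop records with a blank response, and controls might simply fall out. This is partly right: a reader might infer that controls certainly count as exacerbation-free, and the documents do not state it. The better-supported reading still points that way. The RAP's negative binomial model for the same events lists healthy control as a level and promises an estimated yearly rate for that group, which requires controls to enter with counts. If they are instead dropped, the population label is wrong and the analysis set is undefined.

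The second reply is that the final models repair the damage, and this largely stands. In a complete-case COPD-only fit, a null predictor that slipped through the screen still has its P value computed in COPD, so it should look significant in that fit only about 5% of the time. A reader might infer that the reported coefficients or the C-index are biased. That holds only if controls stay in the fit, for example with blank history coded as no and GOLD grade absent, and no C-index effect has been quantified. What remains is that the screen decides which variables enter.

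Third, SAP amendment 3 section 7.1 limits exacerbation summaries and the rate model to COPD and chronic bronchitis, and it does not restate the logistic models. That stands too. However, its section on changes does not withdraw them, and its interim table still lists an exacerbation analysis at month 18.

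Finally, the study is descriptive and the screening threshold is adjustable. This lowers the stakes but does not supply the missing definition.

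**Conclusion.** The point holds as a should-fix on analysis-set definition. RAP amendment 2 places the response, screen and split in a population that includes participants whose outcome is not collected, and it does not say how they are handled.

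If controls enter as event-free, a null ever-smoking predictor passes the 5% screen in about 34% of samples at 20% risk and 53% at 30%, and in about 10% to 86% over risks of 5% to 50%. These figures rest on that coding, the planned group sizes, 70% ever smokers and assumed event risks.

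It would go too far to say that unrelated predictors will pass. This is a raised probability, confined to predictors that separate controls from patients. Nor do the documents support saying that all final models are distorted: the harm falls mainly on selection, and on the mismatch between the people used to select predictors and those used to fit them.

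**What to change.** - In RAP 7.4.1, replace the full population with one named set of participants who have exacerbation follow-up, excluding healthy controls. Use it for the response, univariate screen, split, multivariable fit and C-index, in both the full-population and the sub-cohort models, including the bootstrap test sets.
- Where GOLD grade or COPD exacerbation history is a candidate predictor, use COPD (GOLD I-IV) only from the screen onward. Chronic bronchitis participants have valid follow-up and can be modelled separately if wanted.
- State how blank predictor values are treated, and correct the conflicting population comments in the example programs.
- State in SAP amendment 3 whether these models still apply. The change would bring them into line with its section 7.1.

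The cost is one filter in the programs and a smaller labelled sample: 1,880 planned instead of 2,000, or 1,700 for COPD-only models. The participants removed either have no collected outcome or lack the required predictors.
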